8.9. Withdrawal of Patients from the Study Procedures

Patients must be withdrawn from the study for any of the following:

- Withdrawal of consent
- The patient is unwilling or unable to comply with the protocol

Other reasons for withdrawal of patients from the study Procedures might include:

- At the discretion of the Investigator for medical reasons
- At the discretion of the Investigator or Sponsor for noncompliance
- Significant protocol deviation

All efforts will be made to complete and report the observations as thoroughly as possible up to the date of withdrawal. All information, including the reason for withdrawal from study, must be recorded in the eCRF.

Any patient who withdraws consent, in writing or via verbal communication (documented by study site personnel) to participate in the study will be removed from further treatment and study observation immediately upon date of request. These patients should be encouraged to complete the ETTX visit procedures at the time of withdrawal if patient is in the Treatment Period, or the ETPT visit if patient is in the Post-Treatment Period ([Appendix A](#)). If the patient declines or is unable to participate in the above, the Investigator should clarify what type of follow-up the patient is agreeable to: in person, by phone/mail, through family/friends, via correspondence/communication with other physicians, and/or from review of the medical records. Wherever possible these patients should continue to be followed up via the agreed means to collect information on AEs, concomitant medications and survival status. At the very least, the patient's status at the end of the protocol defined study period should be ascertained and documented wherever possible. The agreed means of follow-up will be documented in the patient records and notified to the Sponsor.

For patients withdrawn for reasons other than withdrawal of consent every effort should be made to complete the Post-Treatment Period and early termination study procedures.

8.10. Concomitant Therapy and Procedures

The use of concomitant therapies or procedures defined below must be recorded on the patient's eCRF. Adverse events related to administration of these therapies or procedures must also be documented on the appropriate eCRF.

8.10.1. Concomitant Therapy

A concomitant therapy is any non-protocol specified drug or substance (including over-the-counter medications, herbal medications and vitamin supplements) administered between signing of informed consent and last visit (PTWk15/ETPT).

Allowed Concomitant Therapy

Any other medications deemed necessary by the Investigator are allowed except those listed in the disallowed concomitant therapy.

In the Post-Treatment Period, approved acromegaly medication may be added for patients with elevated IGF-1 (≥ 1.3) levels in consultation with the Investigator and Sponsor Medical Monitor or Designee.

Disallowed Concomitant Therapy

The following medications or interventions cannot be started during the Treatment Period: other approved or investigational medications for acromegaly (e.g., bromocriptine, cabergoline, pasireotide, quinagolide, octreotide (all formulations), pegvisomant, pasireotide, lanreotide (all formulations), dopamine agonist). If modification of acromegaly medication is considered, the recommendation is to wait until after Week 17 to allow ISIS 766720 to reach steady-state therapeutic concentrations and to ensure patient is on a maximal dose of ISIS 766720 per Section 8.7 prior to initiation of other acromegaly medications.

Use of anti-obesity agents or weight loss programs are not allowed prior to Week 27. Initiation of anti-obesity agents or weight loss programs after Week 27 may be considered after consultation with the Sponsor Medical Monitor or Designee

It is preferred for patients to maintain stable regimens of estrogen containing medications, antidiabetic medications and glucocorticoids throughout the study, however, changes to a stable regimen allowed at Screening may only be considered after consultation with the Sponsor Medical Monitor or Designee.

Any investigational therapeutic drug or device including other marketed agents at experimental dosages/utilities that are being tested—patient will be withdrawn.

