Appendix A. Schedule of Procedures – Post-Treatment Period

Study Period	Post-Treatment Period (14 Weeks)			ETTX ^{1, 2}	ETPT ^{1, 2}
Study Week (Wk) from Last Dose	PTWk5	PTWk9	PTWk15	ETTX ^{1, 2}	ETPT ^{1, 2}
Study Day from Last Dose	PTD29 ²	PTD57 ²	PTD99 ²	NA	NA
Study Day from Day 1	533	561	604	NA	NA
Visit Window ±	7	7	7	NA	NA
Home Health Care Visit Option ³	X	X			
MRI/CT of sellar				X ¹³	
Echocardiogram				X ¹⁴	
AcroQoL			X	X	X
ASTS-M			X	X	X
EQ-5D			X	X	X
SF-36			X	X	X
Ring Size Measurement			X	X	X
Body Weight			X	X	X
Vital Signs ⁴	X	X	X	X	X
Physical Exam ⁵			X	X	X
ECG (12-Lead)			X	X	X
Adverse Events	X	X	X	X	X
Concomitant Medications	X	X	X	X	X
Pregnancy Test ⁶	X	X	X	X	X
Chemistry Panel (Fasting) ^{7, 8}	X	X	X	X	X
Hematology ⁸	X	X	X	X	X
Partial PD Panel: GH, IGF-1, GHBP ⁷	X	X			
Full PD Panel ⁷			X	X	X

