For other endpoints, baseline is defined as the last non-missing value prior to the first administration of ISIS 766720.

Analytical visits:

In general, all post-baseline data will be summarized using the visit labels provided in the data. Multiple results with the same visit label will be averaged for the continuous variables, and the worst result will be used for the categorical variables. Results with visit labels as “Unscheduled” will not be included in the by-visit summary tables and figures except for determining baseline and the incidence of abnormality lab summary including AST, ALT, platelet and renal but will be presented in data listings.

For patients who had last dose prior to treatment termination, PD results greater than 3 weeks after the last dose (the date of last dose + 21 days) up to treatment termination will not be included in the by-visit summary tables and figures. Also, for patients who started other acromegaly medications in the post-treatment period, PD results after the start date of acromegaly medication will not be included in the by-visit summary tables and figures.

Other situations, such as required additional confirmation, will be described separately in the related endpoint analysis approach.

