3.3.5. Incomplete or Missing Data

In general, missing IGF-1 for a scheduled assessment will not be imputed. Patients with missing data for a scheduled assessment time point will be excluded from the summary for that time point.

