3.4.2. Analysis of Secondary Endpoints

The analysis population will be conducted in both FAS and PPS. The results will be summarized by the ISIS 766720 dose received at randomization and overall. In addition, the results will also be summarized by the maximum ISIS 766720 dose received through the study and overall.

Subset analysis will be conducted among uncontrolled population ($IGF-1 > 1.3 \times ULN$ at Day 1) and high-strata IGF-1 population ($IGF-1 > 2.5 \times ULN$ at Screening), separately.

Proportion of subject incidence of achieving within 1.2 times, achieving 1.0 times of ULN over time will be summarized at each scheduled visit respectively. The estimated proportion with 95% confidence interval will be provided.

Absolute, change and percent change from Baseline to each scheduled post-baseline visit in IGF-1 over time will be summarized at each scheduled visit.

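### After treatment, other acromegaly drugs may be started because IGF-1 is elevated and later IGF-1 values are then dropped, so the post-treatment by-visit summaries can overstate the remaining effect

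*Combined protocol and SAP*

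**What the plan says.** Protocol 8.10.1 makes IGF-1 itself the condition for adding a drug: "In the Post-Treatment Period, approved acromegaly medication may be added for patients with elevated IGF-1", with the level given as ≥ 1.3. The wording is permissive, and the decision is taken in consultation with the medical monitor.

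SAP 3.2.1 (analytical visits) then provides, "for patients who started other acromegaly medications in the post-treatment period", that "PD results after the start date of acromegaly medication will not be included in the by-visit summary tables and figures". On missing IGF-1, SAP 3.3.5 adds: "Patients with missing data for a scheduled assessment time point will be excluded from the summary for that time point". SAP 3.2.3 says the same for data in general.

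The affected output is in SAP 3.4.2: "Absolute, change and percent change from Baseline to each scheduled post-baseline visit in IGF-1 over time will be summarized at each scheduled visit", and "Proportion of subject incidence of achieving within 1.2 times, achieving 1.0 times of ULN over time will be summarized at each scheduled visit respectively". Protocol 10.6.3 has change and percent change at each scheduled post-baseline visit analysed in a similar way to the primary analysis, which is a one-sample t-test.

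In the post-treatment schedule (Appendix A), the row "Partial PD Panel: GH, IGF-1, GHBP" is marked at PTWk5 and PTWk9, and the full panel is drawn at PTWk15.

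Two further passages bear on timing. The protocol synopsis moves a patient who needs another acromegaly drug during treatment off study drug and into the Post-Treatment Period. Footnote 5 of Appendix B says IGF-1 results become available from Week 17 and then every three months, or more often at the investigator's judgement.

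**The concern.** Whether a value is dropped depends on an earlier value of the same outcome. A patient whose IGF-1 has risen can be started on another drug and then leaves all later summaries. A patient whose IGF-1 has not risen stays. A plain mean over those who remain is then biased towards more suppression, and a plain proportion within 1.2 or 1.0 × ULN is biased upwards.

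Leaving out values taken on another drug is reasonable in itself. Keeping them would not help, because the new drug also lowers IGF-1. The difficulty is averaging the selected remainder as though it stood for all patients.

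Change and percent change in IGF-1 over time are secondary endpoints, and the three scheduled post-treatment visits supply their off-drug part. The visible text gives no model for these visits, and no display of how many patients were removed for this reason.

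**Working it through.** **Inputs from the documents.** SAP 3.3.3: reduction 27.5%, SD 30%, 12 evaluable per group (36 in all), 10% dropout. Inclusion criterion 4: screening IGF-1 1.3 to 5 × ULN. Protocol 8.10.1: trigger ≥ 1.3.

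**The plan's own figure.** For a two-sided 5% one-sample t-test with effect 27.5/30 = 0.917 SD, the noncentral t gives power 78.2% at n = 11 and 82.4% at n = 12. So 12 is the smallest n reaching 80%, and 36/(1 − 0.10) = 40 randomised. Both reproduce. The documents give no figure for the post-treatment curve.

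**Assumed inputs (not in the documents).** Baseline lognormal with median 2.2 × ULN, cut to 1.3 to 5; 100/70/35% of the effect left at PTWk5/9/15; within-patient CV 12%; after PTWk5 and after PTWk9, each patient at ≥ 1.3 × ULN starts another drug with chance p. There were 3,000 simulated trials of 36 patients per setting. Mean percent change:

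| p | PTWk9 true | PTWk9 as summarised | gap | PTWk15 true | PTWk15 as summarised | gap |
|---|---|---|---|---|---|---|
| 20% | −18.5 | −20.1 | 1.6 | −8.9 | −10.2 | 1.3 |
| 40% | −18.5 | −22.0 | 3.5 | −8.9 | −12.0 | 3.1 |
| 60% | −18.4 | −24.8 | 6.4 | −8.9 | −14.4 | 5.5 |

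With faster fading (90/50/10%) and p of 40 to 60%, the gap at PTWk9 is 15.4 − 13.0 = 2.4 to 17.4 − 13.1 = 4.3. At PTWk15 it is 2.8 − 2.1 = 0.7 to 3.5 − 2.1 = 1.4. A rerun of the 40% setting with baseline log-SD 0.4 and extreme effects clipped gave gaps of 22.6 − 19.2 = 3.4 and 12.6 − 9.6 = 3.0.

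**A different fading model.** Here the effect halves every 8 weeks and half of those seen at ≥ 1.3 start a drug. At PTWk15, 37% of patients are retained, with mean −11.4% against a true −8.0%. The removed 63% must then average (−8.0 + 0.37 × 11.4)/0.63 = −6.0%. The gap is the share removed times the difference between the two groups: 0.63 × (11.4 − 6.0) = 3.4 points. At PTWk9, 61% are retained, and the summary is −15.8% against −13.1% (gap 2.7).

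The proportions move more in relative terms. At PTWk15 the share within 1.2 × ULN is 3.7% in truth and 9.8% as summarised. Nearly all patients within the limit are retained while the denominator shrinks: 3.7/0.37 = 10.0%.

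The wider grid used start chances of 25 to 75%, half-lives of 4 or 8 weeks, reductions of 27.5% or 50%, and baseline–response correlations of −0.3 to 0.6. The summary overstated the effect at PTWk9 and PTWk15 in every setting, by 0.1 to 8 points at PTWk15. Only at a correlation of 0.95 did the percent-change gap fall to about zero or marginally reverse (−15.5 true, −15.4 shown).

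**If the Week 73 value can also trigger a start.** In the 8-week half-life model the gaps become 23.4 − 18.6 = 4.8 at PTWk5, 19.5 − 13.1 = 6.4 at PTWk9 and 13.7 − 8.0 = 5.7 at PTWk15.

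**Does a model recover the truth?** Under the timing in the table, a likelihood analysis conditioning on baseline and earlier post-treatment values was within 0.4 points for p of 20 to 60%, and within 1.1 points at 80%. If drugs start from the Week 73 value, that model stays biased (at 40%, −22.0 against −18.5 at PTWk9). Adding the last on-treatment value removes the bias.

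**The case against.** The strongest case against is about importance. No visible objective or endpoint concerns duration or loss of effect. The synopsis describes the Post-Treatment Period as covering safety, exploratory and PK assessments, and no decision hangs on these visits. That stands, although SAP 3.4.2 and protocol 10.6.3 do bring the visits into the secondary summaries and their one-sample analysis.

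Second, a reader might infer that the late curve consists only of patients who stayed low, and that it certainly exaggerates how long the effect lasts. The documents do not support that. Starting a drug is optional, so patients at or above 1.3 who start nothing remain in the mean. The triggering value precedes the start date and is kept too. If few patients start a drug, little happens.

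Third, start chances, fading rate, baseline median and within-patient CV are all assumed. The gap is also modest beside sampling error: for a 12-patient group after exclusions, with start chances of 20 to 60%, the standard error is about 7.5 to 8.7 points at PTWk9 and 5.7 to 7.5 at PTWk15. The gap exceeds one standard error only for the pooled 36 patients at 60%. This limits the practical weight but does not remove a bias of predictable direction.

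Fourth, some of this will show anyway. Patient numbers accompany every summary, missing visits are summarised, and concomitant medications are tabulated. SAP 3.5 and protocol 10.6.5 are not in the text available, so one cannot claim that no sensitivity analysis exists. But falling numbers alone do not tell the reader why patients left.

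**Conclusion.** The concern holds as a possible overstatement confined to the post-treatment by-visit IGF-1 summaries. Its direction follows from the plan's own rules, apart from an extreme baseline–response correlation. Its size cannot be derived from the documents. The central range of about 1.5 to 6 points at PTWk9 and about 1 to 5.5 at PTWk15 belongs to the slower assumed fade with start chances of 20 to 60%; other settings gave less or somewhat more. PTWk5 is affected only if drugs start before that visit, which the protocol's timing allows.

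A reader might go on to doubt the trial's main efficacy result. That would be wrong: the percent change to Week 27 and the Week 27 normalisation endpoints do not involve this rule. This is an inexpensive improvement to a secondary summary and does not threaten the trial's conclusions.

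**What to change.** In SAP 3.4.2:

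- Keep excluding values after another acromegaly drug is started, and state the target: post-treatment percent change in IGF-1 as if no other drug had been started.
- Estimate it with a likelihood-based repeated-measures model containing visit, randomised dose group (the SAP also summarises by maximum dose, so the grouping must be named), baseline IGF-1, and all IGF-1 values before the start date. Name explicitly the triggering value and the late treatment-period values: Week 73, or the last on-treatment and ETTX values for early stoppers. SAP 3.2.1 separately leaves results more than 21 days after the last dose, up to treatment termination, out of the by-visit tables. ETTX is preferably four weeks after the last dose, so the SAP should say that the model uses the ETTX value.
- Print at each post-treatment visit the number already on another acromegaly drug, beside both the means and the proportions within 1.2 and 1.0 × ULN.
- Keep the observed-case means as supportive.
- State the unit of the 1.3 threshold.

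The cost is a few lines of SAP text and one standard model on data already collected. The model assumes that removal depends only on recorded values, which small dose groups cannot test and which would fail if starts were driven by unrecorded information. The post-treatment curve will probably look somewhat less favourable.

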8.10.2. Concomitant Procedures

A concomitant procedure is any therapeutic intervention (e.g., surgery/biopsy, physical therapy) or diagnostic assessment (e.g., blood gas measurement, bacterial cultures) performed between signing of informed consent and the last visit (PTWk15)

Surgery and radiotherapy for pituitary adenoma during the trial is not allowed (see Section 5.2) and patients who undergo these procedures during the study will be early terminated from the Treatment Period and enter the Post-Treatment Period.

8.11. Treatment Compliance

There is not a patient diary for this trial.

9. SERIOUS AND NON-SERIOUS ADVERSE EVENT REPORTING

9.1. Sponsor Review of Safety Information

Safety information will be collected, reviewed, and evaluated by the Sponsor or Designee in accordance with the applicable Ionis and/or Designee SOPs throughout the conduct of the clinical trial.

9.2. Regulatory Requirements

The Sponsor or Designee is responsible for regulatory submissions and reporting to the Investigators of serious adverse events (SAEs) including suspected unexpected serious adverse reactions (SUSARs) per the International Conference on Harmonization (ICH) guidelines E2A and ICH GCP. Country-specific regulatory requirements will be followed in accordance with local country regulations and guidelines.

Institutional Review Boards (IRB)/Independent Ethics Committees (IEC) will be notified of any SAE according to applicable regulations.

In addition to the Investigator's assessment of relatedness, the Sponsor or Designee will evaluate the available information and perform an independent assessment of all reported SAEs and determine if there is a reasonable possibility that ISIS 766720 is causally related to a reported SAE. While the Sponsor may upgrade an Investigator's decision it is not permissible to downgrade the Investigator's opinion for the purposes of determining whether the SAE meets the definition of a SUSAR.

For the purpose of regulatory reporting of SUSARs, no SAE associated with use of ISIS 766720 is considered expected for this study population.

9.3. Definitions

9.3.1. Adverse Event

An adverse event (AE) can be any unfavorable and unintended sign (including an abnormal laboratory finding, for example), symptom, or disease temporally associated with the use of medicinal (investigational) product, whether or not the AE is considered related to the medicinal (investigational) product.

An AE can therefore be any of the following:

- Any unfavorable and unintended sign (including an abnormal laboratory finding), symptom, or disease temporally associated with the use of a medicinal product, whether or not considered related to the medicinal product
- Any new disease or exacerbation of an existing disease (a worsening in the character, frequency, or severity of a known condition)
- Recurrence of an intermittent medical condition (e.g., headache) not present at Baseline
- Any deterioration in a laboratory value or other clinical test (e.g., electrocardiogram [ECG], X-ray) that is associated with symptoms or leads to a change in study treatment or concomitant treatment or discontinuation from ISIS 766720

Adverse events that are related to a protocol-mandated intervention, including those that occur prior to assignment of study treatment (e.g., screening invasive procedures such as biopsies).

9.3.2. Adverse Drug Reaction and Suspected Unexpected Adverse Drug Reaction

Adverse Drug Reaction (ADR)

In the *pre-approval* clinical experience with a new medicinal product or its new usages, particularly as the therapeutic dose(s) may not have been established, ADR is defined as follows:

All noxious and unintended responses to a medicinal product related to any dose should be considered adverse drug reactions.

The phrase "responses to a medicinal product" means that a causal relationship between the medicinal product and the AE has been determined by the Sponsor as at least a reasonable possibility, i.e., the relationship cannot be ruled out.

Suspected Unexpected Adverse Drug Reaction

A suspected unexpected ADR is any ADR, the nature or severity of which is not consistent with the applicable product information, e.g., Investigator's Brochure for an unapproved medicinal (investigational) product.

A suspected adverse reaction implies a lesser degree of certainty about causality than an adverse reaction.

9.3.3. Serious Adverse Event (SAE)

A SAE is any AE that in the view of either the Investigator or Sponsor, meets any of the following criteria:

- Results in death
- Is life threatening: that is, poses an immediate risk of death at the time of the event
An AE or suspected adverse reaction is considered "life-threatening" if, in the view of either the Investigator or Sponsor, its occurrence places the patient at immediate risk of death. It does not include an AE or suspected adverse reaction that, had it occurred in a more severe form, might have caused death
- Requires inpatient hospitalization or prolongation of existing hospitalization
Hospitalization is defined as an admission of greater than 24 hours to a medical facility and does not always qualify as an AE
- Results in a persistent or significant incapacity or substantial disruption of the ability to conduct normal life functions
- Results in a congenital anomaly or birth defect in the offspring of the patient (whether the patient is male or female)
- Important medical events that may not result in death, are not life-threatening, or do not require hospitalization may also be considered serious when, based upon appropriate medical judgment, they may jeopardize the patient and may require medical or surgical intervention to prevent 1 of the outcomes listed in this definition. Examples of such medical events include allergic bronchospasm requiring intensive treatment in an emergency room or at home, blood dyscrasias or convulsions that do not result in inpatient hospitalization, or the development of drug dependency or drug abuse

The terms "severe" and "serious" are not synonymous. Severity refers to the intensity of an AE (e.g., rated as mild, moderate, or severe, or according to National Cancer Institute Common Terminology Criteria for Adverse Events [NCI CTCAE]; the event itself may be of relatively minor medical significance [such as severe headache without any further findings]).

Severity and seriousness need to be independently assessed for each AE recorded on the eCRF.

